11.4.3 Comparison of muscle function assessment tools

The impact of the choice of muscle function assessment tool will be assessed by comparing the prevalence of undernutrition diagnosed with each tool and by comparing the presence of reduced muscle mass with each tool.

12 Expected results in terms of scientific and professional advances

The results of this study will make it possible to verify whether the GLIM definition increases the prevalence of undernutrition compared to that of the HAS. The use of one or other of the definitions could thus have an impact on the medical and paramedical management of undernutrition. On the other hand, muscle function benefits from various assessment tools. These tools assess different aspects of the muscle, such as strength, functional performance or quantity. Muscle function has an important place in the new definitions of undernutrition, thus involving physiotherapists and EAPAs in addition to dieticians, nurses, care assistants and physicians in the screening for undernutrition. The different tools could lead to a different estimation of the reduction of muscle mass and thus a different prevalence of undernutrition. The results of our study will help to evaluate this and guide professionals in the choice of tools for assessing muscle function.

13 Expected benefits and risks for patients

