Main objective	The main objective of this study is to compare the prevalence of global undernutrition based on the diagnostic criteria recommended by the HAS with that based on the diagnostic criteria recommended by the GLIM, in patients hospitalised in short stay and follow-up and rehabilitation care in diabetology-obesity, pneumology, oncology and gastro-nutrition
Secondary objectives	
The secondary objectives will be, for patients hospitalised in short stay and follow-up care and rehabilitation of diabetes-obesity, pneumology, oncology and gastro-nutrition:
 
 • To compare the prevalence of severe undernutrition between the HAS and GLIM groups; • To compare the morbi-mortality of undernutrition between the HAS and GLIM groups on : 
 ◦ Length of stay ; ◦ Mortality rate ; ◦ Autonomy at discharge. • To evaluate the impact of the choice of muscle function assessment tool on the prevalence of undernutrition in the HAS and GLIM groups.

Research scheme	Prospective, monocentric, interventional cohort study with minimal risks and constraints falling within the scope of article L.1121-1 of the Public Health Code.
Inclusion criteria	
 - Admitted to short stay and follow-up care and rehabilitation of diabetes-obesity, pneumology, oncology and gastro-nutrition; - Age between 18 and 70 years at the time of inclusion ; - Affiliation with a social security scheme or beneficiary of such a scheme ; - Oral, free, informed and express consent of the patient or his/her relative.
Non-inclusion criteria	
 - Inability to perform bioelectrical impedance measurement ; - Patient's refusal to participate in the study ; - Known pregnancy ; - Person subject to a legal protection measure ; - Patient under guardianship or curatorship ; - Patient with limited care ; - Randomisation in the ineligible study group.
Primary endpoint	Prevalence of global undernutrition in patients hospitalised in short stay and follow-up and rehabilitation care for diabetes-obesity, pneumology, oncology and gastro-nutrition, according to the diagnostic methods of the HAS and GLIM

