Secondary evaluation criteria	
 • Prevalences of severe undernutrition according to the HAS and GLIM diagnostic methods; • Morbidity and mortality criteria in the HAS and GLIM moderate and severe undernutrition groups: 
 ○ Duration of hospital stay (days) ; ○ Mortality: proportion and date of occurrence of death among patients included during hospitalisation; ○ Autonomy at discharge: Activities Daily Living score (ADL, Appendix X). • Tools for measuring muscle function : 
 ○ Bioelectrical impedance measurement ; ○ Handgrip ; ○ Walking speed.
Group comparison	Patients hospitalised in short stay and follow-up and rehabilitation care for diabetes-obesity, pneumology, oncology and gastro-nutrition.
Number of subjects needed	260
Expected number of centres	1
Duration of the research	21 months
Statistical analysis of data	Univariate comparisons will use the usual statistical tests after verification of the distribution of the variables (Chi2 or Fisher's test, t-test, anova or their non-parametric equivalents Wilcoxon and Kruskal-Wallis tests). The variables will be compared between the two groups by the appropriate tests according to the type of variables (quantitative or qualitative) and their distribution.
Expected benefits	The results of this study will make it possible to verify whether the GLIM definition increases the prevalence of undernutrition compared to that of the HAS. The use of one or other of the definitions could thus have an impact on the medical and paramedical management of undernutrition. On the other hand, muscle function benefits from different assessment tools, which could lead to a different estimate of the reduction in muscle mass and therefore a different prevalence of undernutrition. The results of our study will help to evaluate this and guide professionals in the choice of tools for assessing muscle function.
Source of funding	Forcilles Hospital-Cognacq-Jay Foundation

Independent Supervisory Committee planned	No
--	----

Table of contents

PROTOCOL VERSION HISTORY.....	3
SUMMARY OF THE RESEARCH.....	4
1 Rationale for the research	10
1.1 Epidemiology and morbidity of undernutrition	10
1.2 Definitions of undernutrition	10
1.3 International consensus on the definition of undernutrition.....	11
1.4 New definition of undernutrition adopted in France.....	11

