3.2 Secondary objectives

The secondary objectives will be, for patients hospitalised in short stay and follow-up care and rehabilitation of diabetes-obesity, pneumology, oncology and gastro-nutrition:

- To compare the prevalence of severe undernutrition according to the HAS and GLIM diagnostic criteria ;
- To compare the morbidity and mortality of moderate and severe undernutrition according to the HAS and GLIM diagnostic criteria :
 - Length of stay ;
 - Mortality rate ;
 - Autonomy at discharge.
- To compare the predictive capacity of muscle function assessment tools on undernutrition according to the HAS and GLIM diagnostic criteria .

4 Outcome

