10.1 Prevalence of undernutrition

Undernutrition is defined according to the diagnostic methods of the HAS and GLIM:

	Phenotypic criteria			Etiological criteria	
	Weight loss (%)	Low BMI (kg/m ²)	Reduction in muscle mass	Reduction in food intake or absorption	Inflammatory situation
GLIM	> 5% in the last 6 months or > 10% beyond 6 months	< 20	Reduction assessed by a validated measurement technique*.	≤ 50% of food intake > 1 week or any reduction > 2 weeks, or any gastrointestinal conditions or symptoms impacting assimilation or absorption	Acute or certain chronic or malignant conditions
HAS	≥ 5% in 1 month or ≥ 10% in 6 months or loss ≥ 10% from usual weight before onset of disease	< 18,5	Quantified Reduction** (QR)	Same as	Same as

For the GLIM and HAS diagnostic method, the diagnosis of undernutrition is positive if an etiological criterion and a phenotypic criterion are present. The assessment of undernutrition according to GLIM will be preceded by a MNA-SF ([Appendix 4](#)). The methods for measuring the reduction in muscle mass are described in section "**7.2.4. Measurement of muscle function**".

Among patients with undernutrition, severe undernutrition is defined by :

	Moderate undernutrition	Severe undernutrition
GLIM	
 • BMI < 20 kg/m² • Weight loss of 5-10% in the last 6 months or 10-20% beyond 6 months • Mild to moderate reduction in muscle mass 	
 • BMI < 18.5 kg/m² • Weight loss of >10% in the last 6 months or >20% beyond 6 months • Severe reduction in muscle mass
HAS	
 • 17 < BMI < 18.5 kg/m² • Weight loss ≥ 5% in 1 month or ≥ 10% in 6 months or loss ≥ 10% from usual weight before onset of disease • Measurement of albumin by immuno-electrometry or immunoturbidimetry > 30 g/L and < 35 g/L. 	
 • BMI < 17 kg/m² • Weight loss ≥ 10% in 1 month or ≥ 15% in 6 months or loss ≥ 15% from usual weight before onset of disease • Measurement of albumin by immuno-electrodelemetry or immunoturbidimetry < 30 g/L

The prevalence of undernutrition is defined as the proportion of patients with moderate and/or severe undernutrition among the patients included in the study.

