11.2 General aspects

Descriptive statistics will be based on means (+/- standard deviation) or medians [interquartile range] depending on the distribution of quantitative variables. Qualitative variables will be described in terms of numbers and percentages. Univariate comparisons will use the usual statistical tests after checking the distribution of the variables (Chi2 or Fisher's test, t-test, anova or their non-parametric equivalents Wilcoxon and Kruskal-Wallis tests). Paired sample tests will be used if necessary.

The tests will be performed at the 5% significance level. The 95% confidence intervals will be provided for each estimate.

The calculations will be done using SPSS v21 IBM and R software (version 3.6.1, <http://www.R-project.org>).

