11.3 Main objective

The difference between the prevalences of global undernutrition between the HAS and GLIM groups will be compared using the McNemar test, designed for the comparison of proportions in matched samples.

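### Section 11.4.3 compares the muscle tools only by how often each is positive, which does not show whether they identify the same patients

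*Combined protocol and SAP*

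**What the plan says.** The analysis of tool choice is one sentence in section 11.4.3: the impact is assessed "by comparing the prevalence of undernutrition diagnosed with each tool and by comparing the presence of reduced muscle mass with each tool". No test is named there. Section 11.2 lists the usual univariate tests and adds "Paired sample tests will be used if necessary". For the HAS–GLIM comparison, section 11.3 says the prevalences "will be compared using the McNemar test, designed for the comparison of proportions in matched samples", and section 11.4.1 reuses that test for severe undernutrition. Sections 11.2 to 11.4.3 plan no cross-classification of the tools, no discordant count and no agreement measure.

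The objective is worded in two ways:

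- Summary, secondary objectives: "To evaluate the impact of the choice of muscle function assessment tool on the prevalence of undernutrition in the HAS and GLIM groups".
- Section 3.2: "To compare the predictive capacity of muscle function assessment tools on undernutrition according to the HAS and GLIM diagnostic criteria".

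Section 12 says of the tools: "These tools assess different aspects of the muscle, such as strength, functional performance or quantity". Both the summary (expected benefits) and section 12 say the results will help "guide professionals in the choice of tools for assessing muscle function". Section 9.2 has impedance, grip strength and walking speed all collected at the inclusion visit, so the measurements are paired within patient. Under section 10.1, for both definitions, "the diagnosis of undernutrition is positive if an etiological criterion and a phenotypic criterion are present". Weight loss and low BMI are phenotypic criteria that do not depend on any muscle tool.

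**The concern.** Two tools can be positive at the same rate in different patients. This is most likely when they measure different things, and section 12 says that these do. A comparison of rates, paired or not, responds only to the difference between the two discordant counts and not to their size.

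Someone choosing a tool needs to know whether swapping one for another changes who is flagged. Equal rates do not answer that. Unequal rates do not answer it either, because they do not show whether one tool's positives contain the other's. The analysis therefore falls short of section 3.2 and of the stated use of the results, although it fits the summary objective.

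**Working it through.** **Inputs.** N = 260 is the planned sample size (section 11.1). It was set for the HAS–GLIM comparison and serves here only as a denominator. The documents give no positivity rate per tool and no sample size for the tool comparison, so there is no plan figure to reproduce. The rate of 20% per tool is an assumption.

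**Reduced-muscle flag.** For two tools let a = both positive, b and c = positive on one only, d = both negative. Each tool flags 0.20 × 260 = 52 patients, so b = c = 52 − a.

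- Rate difference = (b − c)/N = 0, whatever a is.
- The exact McNemar test refers b to a binomial distribution with b + c trials and probability 0.5. With b = c, p = 1.
- Discordant patients = b + c = 2 × (52 − a), from 0 (a = 52) to 104 (a = 0), which is 0–40%.
- At independence the discordant share is 2 × 0.20 × 0.80 = 0.32, and 0.32 × 260 = 83 patients.
- Kappa = (Po − Pe)/(1 − Pe), with Po = (a + d)/N and Pe = 0.20² + 0.80² = 0.68.

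| Overlap | Discordant | Agreement | Kappa | McNemar p |
|---|---|---|---|---|
| Full (a = 52) | 0 | 100% | 1.00 | 1 |
| Half (a = 26) | 52 (20%) | 80% | 0.375 | 1 |
| Independence (expected) | 83 (32%) | 68% | 0 | 1 |
| None (a = 0) | 104 (40%) | 60% | −0.25 | 1 |

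The pattern does not depend on the 20%. At an assumed 30% (78 patients per tool), p is 1 at every overlap, while kappa runs from 1.00 (full) through 0.29 (half) to −0.43 (none).

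**Diagnosis.** A tool can change the diagnosis only in patients who have an aetiological criterion and qualify on neither weight loss nor BMI. Call their share s. With 20% flags that are independent within that group, diagnostic discordance is 0.32 × s:

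- s = 0.30: 0.32 × 0.30 = 0.096, about 10%
- s = 0.50: 0.32 × 0.50 = 0.16, 16%
- s = 0.66: 0.32 × 0.66 = 0.211, about 21%

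The documents do not give s, so 0.30–0.66 is an assumed range.

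A worked case with assumed counts: 60 patients qualify through weight loss or BMI whatever the tool, and each tool adds a different 30. Both prevalences are 90/260 = 34.6% and p = 1. Yet 60/260 = 23% change diagnosis with the tool. Po = 200/260 = 0.769, Pe = 0.346² + 0.654² = 0.547, and kappa = 0.49.

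**The case against.** Much of the plan asks about prevalence. The summary objective, the hypothesis in section 1.8 and the expected results in section 12 all concern whether the tool changes prevalence, and section 11.4.3 answers that. This stands: against the summary objective the analysis is adequate in kind, and agreement is a further question. Section 3.2 and the aim of guiding tool choice do raise that further question, and section 2 presents the tools' predictive capacity as never evaluated or compared.

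The second part of section 11.4.3, on reduced muscle mass, could be read as a patient-level comparison. Section 11.2 also allows paired tests, and a McNemar test is computed from the discordant cells, so the 2x2 table would exist if that test were used. But the plan names no patient-level method for the tools and does not commit to reporting the table.

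A reader might infer three stronger things that the documents do not support:

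- **That a null result will be reported as showing the tools to be interchangeable.** The plan nowhere says so.
- **That the tool could decide the diagnosis in a third of patients.** The 32% is discordance on the muscle flag at an assumed 20% rate. It would carry over to diagnosis only if every patient had an aetiological criterion and none qualified on weight loss or BMI.
- **That the tools could diagnose entirely different patients.** Full separation is possible for the muscle flag. For diagnosis, patients who qualify on weight loss or BMI are common to all tools.

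**Conclusion.** The point holds as a limited one. The planned comparison of rates serves the summary objective. It cannot show whether the tools identify the same patients, so it supports neither the section 3.2 objective nor a recommendation on tool choice. At an assumed 20% per tool, between 0 and 40% of patients could be discordant on reduced muscle mass with no difference in rates, and 32% at independence. For the diagnosis the figure at independence is about 10–21% under the assumed range of s. The actual size depends on rates and overlaps that the documents do not give. The primary analysis is unaffected. This is an inexpensive improvement to one secondary analysis.

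**What to change.** Two points need settling first:

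- **Which tools and cut-offs count as reduced muscle mass under each definition.** The notes to Table 1 in section 1.5 treat grip strength as complementary for GLIM and do not list walking speed there, while the HAS list includes both. Section 10.1 refers both definitions to section 7.2.4, which covers grip and walking speed only. Impedance is in section 8.3, with two indices. These passages must be reconciled before tool-specific GLIM and HAS diagnoses can be derived.
- **The objective.** Align section 3.2 with the analysis. Pairwise agreement is not predictive capacity, so either reword the objective or specify an analysis that addresses it.

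Then, in section 11.4.3:

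- Name a paired comparison of prevalence (McNemar for pairs, or Cochran's Q for all three tools).
- For impedance–grip, impedance–walking speed and grip–walking speed, report the paired 2x2 table, both discordant proportions, positive agreement 2a/(2a + b + c), negative agreement 2d/(2d + b + c), and kappa with 95% CI.
- Do this for reduced muscle mass, the HAS diagnosis and the GLIM diagnosis.
- Give the number of patients with both measurements for each pair. Section 5.2 excludes only those who cannot have impedance, so grip or walking speed may be missing in some.
- Base the conclusion on tool choice on discordance as well as on prevalence.

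The cost is wording plus at least 3 × 3 = 9 tables, and more if both sets of cut-offs or both impedance indices are used. No new measurements or patients are needed. The only downside is a longer secondary analysis.

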13.1 Minimal risks and constraints added by the research

All medical and paramedical examinations and management are usually carried out with the exception of the MNA-SF questionnaire and bioelectrical impedanceometry, which will be carried out systematically in the patients included. The MNA-SF questionnaire is very quick (less than 5 minutes) and therefore causes very little inconvenience to the patient apart from an additional visit by a carer. Bioelectrical impedanceometry is a tool for assessing body composition using electrodes applied to the skin surface. The examination takes an average of 15 minutes, and is non-invasive and painless. The minimal stress is related to the placement of the electrode and the duration of the examination.

13.2 Expected benefits for the patient

This study could highlight a difference in the prevalence of undernutrition according to the definitions and tools used. The results of this study will not provide direct benefits for the patient, but could allow the clinician to be more vigilant if undernutrition is underestimated, according to the criteria used in France. The benefit would then be a broader screening of undernutrition and would allow the adaptation of the patient's nutritional and rehabilitation management.

14 Feasibility

Taking into account the inclusion and non-inclusion criteria, possible refusals of patients to participate in the research, potential exclusions and recruitment experience, we estimate a minimum recruitment capacity of 50% of patients admitted to short-stay and follow-up and rehabilitation care for diabetes-obesity, pneumology, oncology and gastro-nutrition, i.e. 47 patients per month, with a monthly recruitment target of 13 patients over 20 months.

In addition, screening for undernutrition is usually carried out on all patients admitted to these wards within our establishment. Dieticians, nursing assistants, nurses and doctors are therefore trained and used to carrying out this screening. Bioelectrical impedance measurement by dieticians is already performed on some patients, and takes no more than 15 minutes. The addition of this test to the research framework is therefore feasible.

In addition, the teams have experience in clinical research, as they are already involved in other research projects as promoters and investigating centres. The medical and rehabilitation teams are involved in other ongoing research projects (<https://clinicaltrials.gov/ct2/show/NCT02881814><https://clinicaltrials.gov/ct2/show/NCT02474797> and <https://clinicaltrials.gov/ct2/show/NCT04373811>).

15 Ethical and regulatory aspects

The Forcilles-Fondation Cognacq-Jay hospital promoter and the person(s) directing and supervising the research undertake to ensure that this research is carried out in accordance with law n°2004-806 of 9 August 2004 relating to public health policy and the regulatory provisions in force (articles L.1121-1, L.1121-2 and L.1121-3 of the Public Health Code. The data recorded during this research will be subject to computerised processing in compliance with law n°78-17 of 6 January 1978 relating to information technology, files and freedoms, amended by law n° 2018-493 of 20 June 2018 (decree n° 2018-687 of 1° August 2018) and order n° 2018-1125 of 12 December 2018.

The research will be conducted in accordance with this protocol.

15.1 Role of the promoter

The research commission of the Forcilles-Fondation Cognacq-Jay hospital, promoter of this research, submits the file to the opinion of the relevant Comité de Protection des Personnes (CPP) (CPP Ile de France 2) whose opinion will be notified in the information note intended for the persons concerned.

The natural or legal person who initiates the research, manages it and ensures that it is financed is called the sponsor.

15.2 Submission to the PPC

This research will be submitted to a Committee for the Protection of Individuals, which will be drawn by lot within the framework of the "Jardé law" (article L.1121-4 of the Public Health Code, decree no. 2016-1537 of 16 November 2016, which came into force on 18 November 2016).

The opinion of the above-mentioned committee is notified in the information note intended for the persons concerned. A copy of this opinion and a summary of the research will be sent to the ANSM.

15.3 Data protection

This research is subject to law n°78-17 of 6 January 1978 relating to information technology, files and freedoms as amended by law n° 2018-493 of 20 June 2018 (decree n° 2018-687 of 1 August 2018). Information on the rights of persons participating in this research (right of access and rectification, right to object to the transmission of data covered by professional secrecy likely to be used in the context of this research) is included in the information note intended for the patient.

A reference methodology specific to the processing of personal data carried out in the context of biomedical research defined by Law 2004-806 of 9 August 2004 as falling within the scope of Articles L.1121-1 et seq. of the Public Health Code was updated by the CNIL in May 2018 (Deliberation No. 2018-153 of 3 May 2018) following the publication of European Regulation No. 2016/679 (General Data Protection Regulation). This methodology allows a simplified declaration procedure when the nature of the data collected in the research is compatible with the list provided by the CNIL in its reference document. This study is part of the MR001 reference methodology to which the Forcilles-Fondation Cognacq-Jay hospital has committed to comply.

